#### Oxygen Support

- Oxygen Source (room air/oxygen therapy)
- Date & time of assessment
- Name of Procedure (Low flow of oxygen delivery/high flow of delivery)

## Imaging

Type of imaging (CT Scan/X-Ray/MRI/Other)

DMB02-GSOP-RF02 5.0 Statistical Analysis Plan Template 05-Dec-2019
PFIZER CONFIDENTIAL
Page 18
TMF Doc ID: 98.03

- Assessment (Normal/Not evaluable/abnormal)
- If abnormal (Pneumonia without Pleural Effusion/ Pneumonia with Pleural Effusion/Other)

## Hospitalization Details

- Hospitalization Category
- Hospital Duration (Discharge Date Time-Admission Date Time)
- Hospital Ongoing?
- Did the patient have evidence of Acute Respiratory Distress Syndrome (ARDS)?

## Hospitalization Details – Ventilation Details

- Mechanical Ventilation use
- Type of Mechanical Ventilation
- Ventilation duration(End Date Time- Start Date Time)
- Mechanical Ventilation Ongoing?

#### Hospitalization Details – Intensive Care Unit (ICU)

- ICU duration (Discharge Date Time-Admission Date Time)
- Ongoing?

#### Microbiology Culture – Detection RSV SARS

- Specimen Type
- If Nasal Cavity, please provide Directionality
- Method of Test
- Test of Pathogen
- Test Name
- Test Result
- Not Tested

#### Microbiology Culture - Other Respiratory Viruses

- Specimen Type
- If Nasal Cavity, please provide directionality

DMB02-GSOP-RF02 5.0 Statistical Analysis Plan Template 05-Dec-2019
PFIZER CONFIDENTIAL
Page 19
TMF Doc ID: 98.03

- Method of test
- Was pathogen isolated?
- Other pathogen specify

## Microbiology Culture Susceptibility - Pathogen Detection

- Specimen Type
- Method of Test
- Were Isolates Identified?
- Isolate Category
- Isolate Name
- Other Pathogen
- Serotype

## Microbiology Culture Susceptibility - Pathogen Detection

- Antimicrobial Susceptibility Test Drug
- Susceptibility for Drug
- Method to Determine Drug Susceptibility

## Pneumonia Severity Index Scale

- PSI Score
- PSI Grade will be derived from the PSI Score as follows:
  - Grade I: PSI Score=0
  - Grade II: PSI Score=1-70
  - Grade III: PSI Score=71-90
  - Grade IV: PSI Score=91-130
  - Grade V: PSI Score>130

## Survival Follow-up Vital Status

Current subject status (dead/alive)

## Final Diagnosis

DMB02-GSOP-RF02 5.0 Statistical Analysis Plan Template 05-Dec-2019
PFIZER CONFIDENTIAL
Page 20
TMF Doc ID: 98.03

- Final Diagnosis
- If Final Diagnosis is CAP, specify if radiologically confirmed

#### Event Outcome Status

Event outcome status

## Adverse Event Report

- AE ID
- Adverse Event Term
- Is the adverse event still ongoing?
- Severity (Mild/Moderate/Severe)
- Is the adverse event serious?
- Do research related injury criteria apply?
- What was the outcome of this adverse event?
- This event is due to:
  - Other (specify)
- Did the adverse event cause the subject to be discontinued from the study?

## Disposition - Follow-up

- Phase of disposition
- Status of disposition

#### Results of Culture and Urine Assays for S. pneumoniae

Sp+ is defined as the identification of Streptococcus pneumoniae via any of the following three diagnostic methods:

Microbiology culture: As part of standard of care, all blood and respiratory specimens (e.g., blood, pleural fluid, transtracheal aspirate, bronchoalveolar lavage or other respiratory tract specimen) will undergo bacterial culture at the local site laboratory for the identification of S. pneumoniae according to their standard methodology. Results of blood cultures (including antibiotic susceptibility) from this standard of care bacterial culture testing will be recorded in the CRF.

DMB02-GSOP-RF02 5.0 Statistical Analysis Plan Template 05-Dec-2019
PFIZER CONFIDENTIAL
Page 21
TMF Doc ID: 98.03

For sputum specimens collected as part of SOC testing, specimen quality will be assessed using the specimen's standard-of-care Gram stain results. Only bacterial culture results from high-quality sputum specimens will be used in case of categorization for the VE analysis. However, all pneumococcal isolates will be serotyped regardless of specimen quality.

Pneumococcal bacterial isolates from standard of care specimens will be shipped and analyzed in the Pneumococcal Reference Laboratory from the Centro Nacional de Microbiología of the Instituto de Salud Carlos III (ISCIII). The following antimicrobials will be evaluated: penicillin, amoxicillin, cefotaxime, erythromycin, clindamycin, tetracycline, and levofloxacin.

- Binax assay: If a positive result is issued from the urine testing, when analysed by the Pfizer VRD laboratory, then it is considered Sp+. This assay does not provide Sp serotype information.
- UAD assay: The UAD-1 detects 13 serotypes (1, 3, 4, 5, 6A, 6B, 7F, 9V, 14, 18C, 19A, 19F, 23F) used in Pfizer's 13vPnC vaccine. The UAD-2 assay, using the same Luminex xMAP bead technology, detects 11 additional serotypes (2, 8, 9N, 10A, 11A, 12F, 15B, 17F, 20, 22F, 33F). A maximum of two serotypes can be reported from each one of the UADs.

Any participant who is not determined as Sp+ by any of the three diagnostic methods will be considered as Sp-, unless they have missing results from all three diagnostic methods. If any culture identified Sp+, antibiotic susceptibility will be assessed at the local laboratory and results are to be entered in the CRF.

Antibiotic susceptibility and the minimum inhibitory concentrations (MICs) of each isolate will be obtained from local and the National Reference Lab. The data of the local lab will come through the CRF, and those from the National Reference Lab will be maintained in a separate electronic file (non-CRF). We will primarily use the data of the National Reference Lab, and if missing then we will use the data of the local lab.

## Pneumococcal Carriage and RSV Infection Testing

The saliva samples are to be tested for the carriage study. The samples will be collected from all subjects and referred to the Instituto de Salud Carlos III (ISCIII) for culture and molecular biology study (for culture-negative samples). The results of the test will be used to understand the serotype distribution and prevalence in carriage among the study population. Additional PCR testing for RSV and other respiratory viruses will be performed on the same saliva sample to estimate the distribution of CAP events with RSV and also with other respiratory viruses; results will be maintained in a separate electronic file (non-CRF).

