To describe the distribution of S. pneumoniae serotypes using blood, high- quality respiratory cultures, and a serotype- specific urinary antigen detection (UAD) assay among adults 60 years of age and older with CAP.	• Proportion of CAP events for each pneumococcal serotype, PCV-13, and 20-valent pneumococcal conjugate vaccine (PCV20) serotypes among all CAP subjects with UAD1/2 testing (overall) and among all CAP subjects with a pneumococcus identified.	
• To determine the proportion of persons with respiratory pneumococcal carriage among adults 60 years of age and older presenting with CAP by testing saliva specimens using both conventional culture and the sensitive molecular method of PCR for the detection of two target genes (lytA and piaB).	• Proportion of CAP events where the pneumococcus was identified from saliva by culture or PCR divided by all CAP events where the subject had a valid saliva specimen test result.	
• To describe the proportion of participants with CAP and with SP+CAP who present with underlying at-risk and high-risk medical conditions.	• Proportion of CAP subjects with underlying at-risk and high-risk medical conditions, overall and restricted to those with pneumococcus isolated from blood, high-quality respiratory cultures, and a serotype- specific UAD assay.	
• To describe the frequency and type of antibiotic resistance among S. pneumoniae isolates, overall and by specimen type.	• Proportion of S. pneumoniae isolates with antibiotic resistance identified by SOC testing, overall and by resistance type.	

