11.2.3. Pneumococcal Carriage and RSV Infection Testing

The saliva samples will be placed in individual bags for transport and will be kept at room temperature until delivery. Samples will be delivered once or twice a week (preferably at the beginning of the week; Mondays or Tuesdays) to improve the culture efficiency. The samples will be referred to the ISCIII for conventional culture and molecular biology study (for culture-negative samples). Briefly, swabs with the saliva samples will be streaked onto blood agar plates containing gentamicin to select SP and avoid the growth of bacteria from the microbiota. For culture-negative samples, characterization of SP will be performed through a real-time PCR assay for the detection of pneumococcus target genes *lytA* and *piaB*. Once pneumococcus is confirmed, a CST methodology will be used to identify the serotype.

PFIZER CONFIDENTIAL CT45-GSOP-RF152.0 Low-Interventional Study Protocol Template 05-Dec-2019 Page 45 of 70

Additional PCR testing for RSV will be performed on the same saliva sample.

The PI of the ISCIII or designee will be responsible for completing a record with the results of the microbiological tests on the nasopharynx to be submitted to the sponsor regularly. These records will not include any personal data of the participants from whom the isolates were obtained.

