#### 4.8.11. Pneumococcal Carriage Subpopulation

This subpopulation will include the per-protocol population for whom a valid penumoccocal carriage result is available from saliva samples.

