# 6.2.2. Secondary Endpoint 2 - Proportion of respiratory pneumococcal carriage among the CAP population

Proportion of CAP cases where the pneumococcal carriage is identified from saliva by culture or by PCR, divided by all CAP cases where the participants had a valid saliva specimen test result.

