## 6.2.2.1. Secondary Endpoint 2 - Main Analysis

The numerator in this analysis will be the participants with pneumococcal carriage identified from saliva by culture or PCR by reference laboratory. The denominator will be the CAP population and who will have valid carriage results from the reference lab. We will calculate the proportion of participants with pneumococcal carriage of two target genes (lytA and piaB) detected from saliva among this population.

The calculations will also be made by risk status (high-risk, at-risk, and low-risk) and by age group (60-74 years, 75-84 years and ≥85 years).

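### SAP 6.2.2.1 plans a lytA/piaB proportion over everyone with a valid saliva result, but PCR is run only on culture-negative samples; read literally, that figure is too low, while the culture-or-PCR endpoint is unaffected

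*SAP*

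**What the plan says.** **Testing sequence.** SAP 3.4 (Pneumococcal Carriage and RSV Infection Testing) refers saliva for "culture and molecular biology study (for culture-negative samples". Protocol 11.2.3 agrees: "For culture-negative samples, characterization of SP will be performed through a real-time PCR assay for the detection of pneumococcus target genes", namely lytA and piaB. PCR for pneumococcus is thus a second step, taken only when culture is negative.

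**Endpoint.** The protocol's table of secondary objectives and endpoints defines "Proportion of CAP events where the pneumococcus was identified from saliva by culture or PCR divided by all CAP events" with a valid saliva result. SAP 6.2.2 has the same composite: "Proportion of CAP cases where the pneumococcal carriage is identified from saliva by culture or by PCR". SAP 6.2.2.1 sets the numerator as "participants with pneumococcal carriage identified from saliva by culture or PCR by reference laboratory", and the denominator as the CAP population with a valid carriage result from that laboratory.

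**Additional statistic.** SAP 6.2.2.1 then adds: "We will calculate the proportion of participants with pneumococcal carriage of two target genes (lytA and piaB) detected from saliva among this population". It repeats its calculations by risk status and age group.

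**Validity.** SAP 4.8.11 admits participants "for whom a valid penumoccocal carriage result is available from saliva samples". No section says what makes a carriage result valid. SAP 4.8.1 and 4.8.2, by contrast, list the acceptable values for UAD and Binax.

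**The concern.** A detected gene is a PCR result. Under the two-step scheme only culture-negative samples can have one, yet the gene proportion is to be taken over culture-positive samples as well. The participants whose carriage is best established would be counted as if the genes had been sought and not found.

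The objective names PCR as the sensitive method of the two. A reader of the report would take a lytA/piaB percentage over all sampled participants as PCR carriage prevalence, and could find it below the culture percentage. In the risk and age breakdowns, groups with equal carriage but different culture yield would appear to differ.

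**Working it through.** Neither document states a carriage rate, a culture yield or a sample size for this endpoint, so there is no figure to reproduce. The structure can be checked by algebra; **all numerical inputs below are assumed**.

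Inputs:
- *c*: share of valid samples that are culture-positive (assumed 5–20%)
- *q*: share of culture-negative samples that are PCR-positive (assumed 5–20%)
- *s*: share of culture-positive samples that PCR would also have detected (assumed 0.9–1.0)

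Formulas:
1. Composite endpoint (culture or PCR) = *c* + (1 − *c*)*q*
2. lytA/piaB over the full denominator, as the sentence reads = (1 − *c*)*q*
3. lytA/piaB if every sample had PCR = *cs* + (1 − *c*)*q*
4. Shortfall, (3) − (2) = *cs*
5. PCR yield among samples actually PCR-tested = *q*

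Example with *c* = 10%, *q* = 10%, *s* = 1.0:
- Composite: 0.10 + 0.90 × 0.10 = 19.0%
- Gene proportion as written: 0.90 × 0.10 = 9.0%
- Gene proportion with PCR on all: 0.10 × 1.0 + 0.90 × 0.10 = 19.0%
- Shortfall: 10.0 percentage points, or 0.10/0.19 = 53% relative
- Yield among PCR-tested: 10.0%

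Range over the assumed inputs:
- Smallest relative shortfall (*c* = 5%, *q* = 20%, *s* = 0.9): 0.045/0.235 = 19%
- Largest (*c* = 20%, *q* = 5%, *s* = 1.0): 0.20/0.24 = 83%

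Subgroups. Take two groups that both have 20% carriage, assume PCR finds every carrier, and let culture find 30% of carriers in one and 70% in the other. The gene proportion as written is 20% × 0.70 = 14% in the first and 20% × 0.30 = 6% in the second. The gap comes only from the testing sequence. In the second group culture alone gives 20% × 0.70 = 14%, above the 6% gene figure. The composite is 20% in both.

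Formula (1) does not involve *s*. A further PCR on a culture-positive sample could not change its status as a carrier, so the two-step scheme leaves the composite unchanged.

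**The case against.** The strongest reply is that the endpoint is sound. Both documents define carriage as culture or PCR, and the first sentence of SAP 6.2.2.1 puts culture-positive participants in the numerator. Culture first, with PCR on the negatives, is a coherent way to measure that. This stands. A reader might infer that the carriage endpoint is understated because PCR is restricted; the documents do not support that.

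A second reply is that the disputed sentence only restates the composite, echoing the two genes named in the objective. That reading is possible, and under it no carrier is lost. It is the weaker reading, because the preceding sentences have already fixed the composite's numerator and denominator. It would also describe culture-positive participants as gene detections when no gene test was run on them. A programmer could build either table.

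A reader might also infer that the SAP accepts a culture-negative sample with no PCR result as a valid negative. It contains no such rule. Validity is undefined, and SAP 5.3 removes participants from analyses for which their data are missing, so exclusion is an equally natural reading. Nothing in the documents suggests that PCR results will in fact be missing.

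Finally, the endpoint is descriptive, SAP 5.1 applies no hypothesis test, and the size rests on assumed inputs. All true. This limits the consequence to a misleading reported percentage and its breakdowns.

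**Conclusion.** The point holds for one planned statistic. As written, the lytA/piaB proportion over all participants with a valid carriage result excludes culture-positive carriers from its numerator by design, so it is not a PCR carriage prevalence. It is too low by *cs*, the share of samples that culture detects and PCR would also have detected. That amount cannot be derived from the documents; the 19–83% relative shortfall holds only for the ranges assumed above. The conclusion rests on the literal reading of the last calculation sentence of SAP 6.2.2.1 and on the testing sequence that both documents state. The composite endpoint is not affected. The missing definition of a valid carriage result is a supporting clarification and not an error in itself.

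**What to change.** In SAP 6.2.2.1, replace the gene sentence with two statements:
- The carriage proportion counts a participant as a carrier if culture is positive, or if culture is negative and PCR is positive, over all valid samples.
- lytA/piaB positivity is reported only among PCR-tested culture-negative samples, labelled as added yield over culture. The label matters: in the two-group illustration this yield is 14/94 = 14.9% and 6/86 = 7.0%, so it too is not a carriage prevalence.

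As a clarification, define a valid carriage result as culture-positive, or culture-negative with PCR completed, and apply it in SAP 4.8.11 and 6.3.8.

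This changes SAP wording only and needs no extra testing. The cost is that culture-negative samples without a PCR result leave the denominator. If there were many, the composite would drift upward, because culture-positives are always kept. In the example, per 1,000 samples with 10% of the 900 culture-negatives lacking PCR at random, it becomes (100 + 81)/(100 + 810) = 19.9% against 19.0%. Counting those samples as negative would give 181/1,000 = 18.1%. Reporting how many samples are dropped lets the reader judge whether this matters.

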#### Results of the Respiratory Specimens for Viral Testing

DMB02-GSOP-RF02 5.0 Statistical Analysis Plan Template 05-Dec-2019
PFIZER CONFIDENTIAL
Page 22
TMF Doc ID: 98.03

Results of SOC testing for viral pathogens in respiratory specimens collected upon admission will be documented in the CRF. This includes documentation of COVID-19 results when available. SOC viral testing results via PCR and/or viral culture will also be documented. For RSV and COVID-19, both negative and positive test results will be documented.

## Final Diagnosis and Event Outcome

The data on the final diagnosis will include:

- Community acquired pneumonia (CAP)
- Acute Bronchitis
- Exacerbation of COPD.
- Empyema/lung abscess.
- Other Acute Lower Respiratory Infection.
- Acute pulmonary exacerbation of congestive heart failure.
- Non-infectious process

If final Diagnosis is CAP, please specify if radiologically confirmed:

- Confirmed
- Not confirmed
- Not done

Event outcome status at 30 days after admission will include:

- Fatal/deceased.
- Not recovered/not resolved.
- Recovered/resolved.
- Recovered/resolved with sequelae.
- Recovering/resolving.
- Unknown.

The following table will be produced with the Final Diagnosis and Event outcome

Final Diagnosis Event Outcome

	Fatal/deceased N (%)	Not recovered/ not resolved N (%)	Recovered/ resolved N (%)	Recovered/ resolved with sequelae N (%)	Recovering/ resolving N (%)	Unknown N (%)
Community acquired						
pneumonia (CAP)						
Acute Bronchitis.						
Exacerbation of COPD						
Empyema/lung abscess						
Other Acute Lower						
Respiratory Infection						
Acute pulmonary						
exacerbation of						
congestive heart failure						
Non-infectious process						

#### 3.5. Safety Endpoints

An AE is defined as any untoward medical occurrence and can therefore be any unfavorable and unintended sign (including an abnormal laboratory finding), symptom, or disease, whether or not related to the patient's participation in the study. This study does not include interventions that pose more than a minimal risk or burden to the study participants. Adverse events and important research-related injuries (RRI) will be reported in CRF.

AEs and RRIs data will be coded using MedDRA dictionary. The SOC and preferred term will be reported.

## 4. ANALYSIS SETS (POPULATIONS FOR ANALYSIS)

#### 4.1. Study Size

This is a low interventional, multicentre, prospective, hospital-based surveillance study in adults aged 60 years of age or older hospitalised with CAP at participating hospital sites. Based on a sample size calculation, it is estimated to enroll 2,000 to 5,500 participants, which is expected to take 1.7 - 4 years. Since the required number of participants is dependent on the proportion of CAP cases that are VT-CAP and the proportion of the population vaccinated, the required sample size may be adjusted based on ongoing information from laboratory test results and vaccine exposure data, if needed.

## 4.2. All Enrolled Population

The all enrolled population is the full analysis set consisting of all participants enrolled in the study. Any participants who were consented and recorded in the database with a subject ID are considered as 'enrolled'. Participants' disposition and demography will be presented for this population, as well as other population, if needed.

## 4.3. Per-Protocol Population

The per-protocol population consists of all participants in the all enrolled population who met all inclusion/exclusion criteria. Any participant who is included in the 'all enrolled population' will be excluded from per-protocol population if the participant did not meet the inclusion/exclusion criteria. A participant with an important protocol deviation as ascertained by the clinical team will also be excluded from the per-protocol population.

## 4.4. All Hospitalized CAP Population for Incidence Calculations

The hospitalized CAP population for incidence calculation will include:

- Enrolled patients residents in the catchment area of the hospitals meeting inclusion and exclusion criteria and with final diagnosis of CAP from eCRF; and
- Unenrolled patients residents in the catchment area of the hospitals meeting inclusion criteria 1, 2, 4 and no exclusion criteria from the Screening Log and with final diagnosis of CAP.

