9.1.1. Inclusion Criteria

Patients must meet all of the following inclusion criteria to be eligible for inclusion in the study:

- 1. Age ≥ 60 years.
- 2. Evidence of pneumonia within first 48 hours of hospital admission based on:
 - a. Documented pneumonia diagnosis or clinical suspicion of pneumonia* at the time of enrollment **OR**;
 - b. Radiologic findings consistent with pneumonia (eg, increased pulmonary density due to infection and/or alveolar infiltrates [multilobar, lobar, or segmental]) **AND** presence of ≥2 of following 10 clinical signs or symptoms:
 - i. fever (oral temperature >38.0°C or tympanic temperature >38.5°C);
 - ii. hypothermia (<35.5°C measured by a healthcare provider) within 24 hours before enrollment;

iii. chills or rigors;

iv. pleuritic chest pain;

- v. new or worsening cough;
- vi. sputum production;
- vii. dyspnea (shortness of breath);

viii. tachypnea (respiratory rate >20/min);

- ix. malaise; or
- x. abnormal auscultatory findings suggestive of pneumonia (rales or evidence of pulmonary consolidation including dullness on percussion, bronchial breath sounds, or egophony).
- 3. Evidence of a personally signed and dated informed consent document indicating that the patient (or a legally acceptable representative) has been informed of all pertinent aspects of the study.

*Note: Pneumonia may be clinically suspected, based on any combination of radiologic and laboratory findings as well as signs, symptoms and other clinical findings, regardless of a formal admission diagnosis or other diagnoses assigned during hospitalization and other acute or chronic comorbidities, including other pulmonary diagnoses.

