9.1.2. Exclusion Criteria

Patients meeting any of the following criteria will not be included in the study:

- 4. Any patient who develops signs and symptoms of pneumonia after being hospitalized for ≥48 hours (either at current hospital, another transferring hospital, or a combination of these).
- 5. Previously enrolled subjects readmitted ≤ 14 days after discharge for their study qualifying admission.
- 6. At the time of enrolment, pneumonia has been excluded as the diagnosis or another diagnosis confirmed.

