10.2. Screening/Enrolment Log

- The study screening log will be completed by site personnel and be forwarded to the sponsor or its representatives weekly for the required study monitoring and follow-up. The registry will include the following information as permitted by the Independent Ethics Committee (IEC) and may include:
 - Screening date;
 - Hospital site and ward;
 - Sex;
 - Nationality;
 - Surveillance area resident (yes/no);
 - Eligibility if not eligible, why;

- Consented (yes/no);
- Date of consent (day/month/year);
- If declined, reason not consented;
- Study participant ID;
- Date of admission to hospital (day/month/year);
- Year of birth;
- Pneumonia confirmed by Chest radiology (yes/no);
- ICU admission (yes/no);
- Samples collected.

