10.4. Visit 2 Day 30 (Final Diagnosis and Event Outcome)

The participant will be followed-up by telephone at 30 to 45 days after hospital admission. The date of the visit, the patient's final diagnosis and outcome for study-qualifying suspected CAP event will be recorded in the eCRF. If patient returns to study hospital for a standard - of care clinic visit for another reason, the visit may occur in person. RRIs will be collected if encountered during the collection of visit-related information or if the patient is contact by phone.

- The following data will be recorded in the study eCRF:
 - Any additional results from standard –of care pneumococcal and viral respiratory testing, including COVID-19 and RSV, that was not captured during Visit 1.
 - Additional information on hospitalisation data eCRF items not captured during Visit 1.
- Principal investigator (PI) or designee should make an outcome assessment of final diagnosis based on any information available over the hospitalisation of the patient. This may include both study and SOC exams, procedures and tests. This data point can be recorded on Day 30 or sooner if available. Final diagnosis categories will include:
 - CAP-radiologically confirmed;
 - CAP-not radiologically confirmed (eg, clinical CAP);
 - CAP-no chest radiology done; or
 - Other diagnosis (not CAP).
 - Acute Bronchitis.
 - Exacerbation of COPD.
 - Empyema/lung abscess.
 - Other Acute Lower Respiratory Infection. PFIZER CONFIDENTIAL CT45-GSOP-RF152.0 Low-Interventional Study Protocol Template 05-Dec-2019 Page 39 of 70

- Acute pulmonary exacerbation of congestive heart failure.
- Non-infectious process.
- Event disposition at 30 days after admission:
 - Fatal/deceased.
 - Not recovered/not resolved.
 - Recovered/resolved.
 - Recovered/resolved with sequelae.
 - Recovering/resolving.
 - Unknown.
- Vital Status (ie, deceased or living), including date and cause of death if deceased.
- RRIs per Section 16.2 and selected exposures and AEs related to Pfizer products per Section 16.3.

Case Definition for Radiologically Confirmed CAP

Patients in whom the treating physician clinically suspected pneumonia who meet the following 2 criteria will be considered to have radiologically confirmed CAP:

- 1. Has a radiologic finding that is consistent with pneumonia (eg, pleural effusion, increased pulmonary density due to infection, the presence of alveolar infiltrates [multilobar, lobar or segmental] containing air bronchograms); AND

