12.1.3.5. Incidence CAP Population (Exploratory Analysis Population)

The calculation of incidence will include all CAP events identified on the screening log as residents of the hospitals' geographical catchment area either prospectively or retrospectively through ICD discharge code review.

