#### 6.3.1.1. Exploratory Endpoint 1 - Main Analysis

The incidence rate of CAP  $(IR_{CAP})$  will be calculated as

$$IR_{\textit{CAP}} = \frac{\textit{no. of CAP cases in the screening log} \div \textit{no. of years of surveillance}}{\textit{total population of the hospitals' geographical catchment area}} \times 100,000$$

The no. of years of surveillance will be calculated as

(date of last person 1st visit – date of the start of the surveillance period +1)/365.25

Note that the date of start of surveillance will be obtained from the Clinical Scientist of this study based on the data that it is confirmed that all pneumonia cases are being captured on the screening log.

DMB02-GSOP-RF02 5.0 Statistical Analysis Plan Template 05-Dec-2019
PFIZER CONFIDENTIAL
Page 36
TMF Doc ID: 98.03

We will compute distribution of the following variables between cases obtained from eCRF (enrolled patients) and Screening Log (not included in the eCRF/not enrolled) to evaluate the representativeness of the enrolled cases:

- Age
- Sex
- Nationality
- Radiologically confirmed CAP
- ICU Status

We will perform chi-square or Fisher's exact test, as appropriate, for the categorical variable and Student's T-test or Wilcoxon-Mann-Whitney test, as appropriate, for the continuous variables to evaluate the differences between the two populations (enrolled versus not enrolled).

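### SAP 4.4 requires a final CAP diagnosis for unenrolled patients that no listed source records, so the exploratory CAP incidence is probably modestly overstated

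*SAP*

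**What the plan says.** SAP 4.4 builds the incidence numerator from two groups of catchment residents. Enrolled patients must meet the entry criteria and have a final diagnosis of CAP, with the eCRF named as its source. The second group is "Unenrolled patients residents in the catchment area of the hospitals meeting inclusion criteria 1, 2, 4 and no exclusion criteria from the Screening Log", again with a final diagnosis of CAP, but here no source is named for the diagnosis.

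The SAP's version history ties it to Protocol v3.0. In that protocol, section 9.1.1 lists three inclusion criteria, the last being "Evidence of a personally signed and dated informed consent document". Numbering continues into the exclusions, so item 4 now reads "4. Any patient who develops signs and symptoms of pneumonia after being hospitalized for ≥48 hours" (section 9.1.2).

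Protocol 10.4 places the diagnosis at Visit 2, where the "Principal investigator (PI) or designee should make an outcome assessment of final diagnosis", recorded in the eCRF. The log fields in Protocol 10.2 cover eligibility, residence, site, year of birth, ICU admission and chest-radiology confirmation. None is a final diagnosis.

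Elsewhere the numerator carries no such condition. Protocol 12.1.3.5 states: "The calculation of incidence will include all CAP events identified on the screening log as residents", found prospectively or by discharge-code review. Protocol 12.4.2 and SAP 5.2.4 agree, and the SAP 6.3.1.1 formula uses "no. of CAP cases in the screening log".

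**The concern.** Entry is possible on clinical suspicion alone (inclusion criterion 2a), and Visit 2 provides for diagnoses other than CAP. Exclusion 6 removes only patients whose alternative diagnosis was settled by enrolment. Some suspected cases will therefore turn out not to be CAP. SAP 4.4 removes them if they were enrolled, but the listed data give no means of removing them if they were not. One rate then mixes a confirmed count with an unconfirmed one.

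A programmer also has two rules to choose between: the SAP 4.4 definition, which cannot be applied as written to unenrolled patients, and the unconditional log count used elsewhere.

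The choice carries forward. Under Protocol 12.4.2 the SP+CAP and radiologically confirmed rates are enrolled proportions multiplied by the CAP rate, and the risk-group rates in SAP 6.3.4 also start from the log count.

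**Working it through.** **Step 1: is there a source for the diagnosis?**
- Visit 2 and the eCRF cover participants only.
- The log fields in Protocol 10.2, and the log description in SAP 2.2.2, contain no final diagnosis.
- SAP 2.2.3 names the log, the reference laboratory and local sources as non-CRF data. Local sources are described as giving population counts.
- Chest-radiology yes/no cannot stand in, because SAP 4.5 counts CAP that was not radiologically confirmed or had no imaging.
- Discharge-code review (Protocol 12.4.2) is described as a monthly check for missed events, not as a way of confirming logged ones.

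**Step 2: reproduce the unenrolled share from Protocol Table 6.** CAP inpatients = enrolled / share enrolled.
- Scenario 2: 1960/0.70 = 2800, as stated; unenrolled 30%.
- Scenario 12: 1960/0.50 = 3920, as stated; unenrolled 50%.
- Scenario 13: 1960/0.30 = 6533, as stated; unenrolled 70%.

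**Step 3: size of the overcount.** Let u be the unenrolled share of logged suspected CAP and f the fraction of suspected CAP that is not CAP, taken as equal in both groups. Per suspected event, the true count is 1 - f. The count obtained is (1 - u)(1 - f) + u. The relative overstatement is

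[(1 - u)(1 - f) + u]/(1 - f) - 1 = u·f/(1 - f).

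The documents give no value for f, so 5-15% is an assumption.

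| u | f = 5% | f = 10% | f = 15% |
|---|---|---|---|
| 30% | 0.015/0.95 = 1.6% | 0.030/0.90 = 3.3% | 0.045/0.85 = 5.3% |
| 50% | 0.025/0.95 = 2.6% | 0.050/0.90 = 5.6% | 0.075/0.85 = 8.8% |
| 70% | 0.035/0.95 = 3.7% | 0.070/0.90 = 7.8% | 0.105/0.85 = 12.4% |

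**Step 4: compare with the reported precision.** As an illustration, take 1,800 CAP admissions a year (Protocol 12.1.2), all in residents, for 4 years, and 103,844 people aged 60 or over (Protocol 9.1).
- 7200/4/103,844 × 100,000 = 1,733 per 100,000 per year.
- Exact Poisson 95% limits (SAP Appendix 3.2) are 1,694 to 1,774, about ±2.3%.
- A 1.6% overcount gives 1,761, inside those limits. A 5.3% overcount gives 1,825, outside them.

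**The case against.** A reader might infer that the stale number empties the unenrolled group: item 4 is now an exclusion, so nobody could meet it and also meet no exclusion, and incidence would fall by 30-70%. The documents do not support this. SAP 4.4 names inclusion and exclusion criteria separately. The protocol's amendment history indicates that deleted inclusion criterion 4 concerned catchment residence, which the same bullet requires and the log records. The reference is a redundant leftover.

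Other points for the plan have weight:
- The log field list is permissive, so a diagnosis item could be added. Discharge codes are a plausible source for unenrolled patients. If they were applied to all of them, the overcount would shrink. Neither use is stated.
- SAP 4.4 can be read as defining which events qualify and 6.3.1.1 as the formula applied to them. That reading removes the conflict but leaves the condition impossible to apply to unenrolled patients on the listed data.
- The 30%, 50% and 70% shares are planning inputs for an immunocompetent VE sample. By footnote c of Table 6 they include patients missed through incomplete surveillance, some of whom may never reach the log.
- SAP 6.3.1.1 compares enrolled with unenrolled patients on five characteristics. Final diagnosis is not one of them.
- The protocol calls its incidence estimates conservative because of under-ascertainment. That acts in the opposite direction, but it does not correct an overcount.

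**Conclusion.** The point holds as a gap in the definition of an exploratory numerator. SAP 4.4 cites a criterion that no longer exists, harmlessly on its natural reading, and sets a diagnosis condition that can be applied to enrolled patients but, on the listed data, not to unenrolled ones.

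The likely result is a modest overstatement of CAP incidence and the rates built on it: about 1.6-5.3% at the planned 30% unenrolled, rising to about 12% at 70%. This assumes that 5-15% of suspected CAP is not CAP, that the fraction is the same in both groups, and that no diagnostic filter is applied to unenrolled patients. It is the effect of this mechanism alone, not the net error after under-ascertainment. The primary VE analysis is unaffected. The correction should be made before incidence is programmed.

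**What to change.** In SAP 4.4, define the unenrolled group as catchment residents meeting inclusion criteria 1 and 2 and no exclusion criterion. Then confirm CAP by source:

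- **Logged prospectively, no discharge diagnosis available:** multiply the count by the proportion of enrolled participants with a final diagnosis of CAP, within strata the log records (age, chest radiology yes/no, site). SAP 6.3.4.1 already applies enrolled proportions to unenrolled patients for risk groups.
- **Pneumonia ICD discharge code available:** accept the code as the CAP diagnosis and do not scale. Scaling these events would discount them by a rate derived from suspicion at admission and understate incidence.

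Use this same numerator in SAP 5.2.4 and 6.3.1.1, and report the unscaled count as a sensitivity analysis.

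The cost is SAP wording and a stratified multiplication, with no new data. The small downside is the assumption that enrolled and unenrolled patients have the same confirmation rate within a stratum. A scaled numerator is also no longer a pure count, so the interval should carry the uncertainty of the estimated proportion as well as the Poisson limits of Appendix 3.2.
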